## 5. TREATMENT OF SUBJECTS

### 5.1 Investigational product/treatment

#### 5.1.1 Intervention: Aggression

In this study, the internet-based intervention 'Aggression' is evaluated. This intervention is part of the eHealth-platform Minddistrict. Minddistrict is a platform that offers over 300 different internet-based interventions, primarily targeted at mental healthcare. The platform contains a broad range of interventions, focused on for example attention deficit hyperactivity disorder (ADHD), mindfulness, autism, healthy lifestyle, and depression. These interventions are used by over 250.000 people in Europe. The entire Minddistrict platform is certified as ISO 27001:2017 and NEN 7510-1:2017 and is certified as a medical device under the Dutch Law on Medical Devices.

All internet-based interventions of Minddistrict via the 'Intervention Mapping' approach [40]. Intervention Mapping is as a planning approach which uses theory and evidence as foundations for taking an ecological approach to intervening in health problems, following a systematic approach. Minddistrict also uses behavioural change techniques, or BCTs. These techniques are specific components designed to change behaviour, such as goal-setting, feedback or behavioural practice and rehearsal. Furthermore, persuasive design methods are applied. By incorporating persuasive features such as personalization, reminders or rewards, the chances of people being adherent to the internet-based intervention and consequent attitude and behaviour change increase. By combining BCTs and persuasive features, attention is paid to the content and design of Minddistrict interventions.

This RCT is focused on the internet-based intervention 'Aggression'. This intervention is used a blended way, i.e. integrated in face-to-face treatment. In this intervention, patients learn to deal with conflict and triggers in a constructive way. The intervention is focused on three main objectives: (1) increasing the motivation to change, (2) acquiring skills for dealing with conflict, and (3) breaking the cycle of aggression by providing knowledge on situational, emotional, cognitive and physical triggers. The module consists of 10 lessons:

1. **Motivation – where are you now?** In this lesson, the patient is introduced to the module, amongst other things by means of a video with a therapist and an audio fragment of an expert by experience. The advantages and disadvantages are discussed by means of open-ended questions.
2. **Where do you want to go?** In this lesson, the patient is asked to think about the future with and without aggression. They are asked about their goals by means of open-ended questions, on which feedback is provided by the therapist. Finally, the patients works on a diary by means of a daily reminders in which they can monitor their own aggressive behaviour and accompanying triggers.

3. **Circle of aggression.** In this lesson, the patient is informed about the circle of aggression by means of written text, illustrations and a video. Next, the patient thinks about their own risk situations and accompanying triggers.
4. **Thoughts.** In this lesson, the patient receives information about convictions about their past and thinking styles by means of videos, written texts and short assignments. Attention is paid to different perspectives, convictions, thinking errors and the challenging of thoughts.
5. **Emotions.** This section starts with information on emotions by means of text and animation. Next, different gradations of emotions are explained, using the metaphor of (over)cooking pans. Via videos, the patient learns about emotions that can lead to aggression.
6. **Bodily sensations.** In this lesson, the patient learns more about bodily sensations and risky behaviours that are related to aggression by means of assignments. Additionally, attention is paid to relaxation exercises to deal with bodily sensations.
7. **Techniques for self-control.** In this lesson, the patient works on their coping skills and self-efficacy for preventing aggression. The patient learns about potential coping skills such as avoidance, stepping out of the situation and time-outs by means of text and videos with experts by experience.
8. **Asking for help.** In this lesson, the patient learns how to ask for help from others and gains insight via text and video on how to deal with others. Furthermore, the patient is encouraged to practice with these coping strategies in real life.
9. **Assertiveness.** In this lesson, the patient gains knowledge about reacting in sub-assertive, assertive and aggressive ways. By means of quizzes, text and videos, the patient learns about and can practice with coping skills to deal with aggression.
10. **Relapse-prevention.** In the final lesson, the patient learns about relapse prevention plans via texts and videos with experts by experience. The patient creates their own relapse prevention plan and makes plans for their future.

As can be seen, each lesson consists of multiple components, i.e. written text, assignments and videos with therapists and/or experts by experience. After completing each lesson, the patient is rewarded by means of a 'milestone'. Furthermore, after each lesson, the therapist sends written feedback on the assignments to the patient. Because 'Aggression' is a blended intervention, each lesson is briefly discussed in an in-person treatment session. This means that generally, participants work on one lesson per week. See the Appendix for screenshots of 'Aggression'.

The internet-based module Aggression was developed in 2012 and has been used for approximately 10 years in different branches forensic mental healthcare. Recently, the

intervention has been updated cosmetically to ensure it is in line with current insights in terms of content and design. However, as is the case for most internet-based interventions in Dutch mental healthcare, it hasn't been evaluated on effectiveness. Several years ago, a mixed-methods study on the use of Minddistrict modules in Dutch forensic psychiatric outpatient care was conducted [21]. This study showed that Aggression was one of the most-used interventions of the Minddistrict platform within this organization – Transfore. However, interviews and data on usage showed that there is still much room for improvement in terms of uptake. One of the main reasons for this was that while therapists were able to identify benefits and expressed an intention to use the intervention, they often did not think about using the intervention because it was 'not in their system'. Additionally, if a patient started, therapists often did not integrate the intervention in treatment because of the same reason: they forgot about it. In order to increase the uptake of 'Aggression' in this study, therapists will be supported in remembering to introduce and keep on discussing the intervention with the patient. Finally, in qualitative research, therapists mentioned that limited evidence of these interventions was a barrier for their usage: if they do not know if the intervention works and is evidence-based, they indicated that they are less prone to use it [19, 21]. In line with this, therapists expressed a need for evaluation studies on internet-based interventions in treatment of forensic psychiatric patients to overcome this barrier. Consequently, based on these qualitative findings, it is expected that especially those therapists that require more research are intrinsically motivated to participate – which is underlined by observations from conversations with therapists that are eligible to participate.

### **5.1.2 Treatment as usual**

In this study, the control group will receive treatment as usual. In general, this refers to any form of psychotherapy that is delivered by a licenced psychologist to a patient in a one-on-one setting. The main focus of treatment as usual should lie on aggression regulation. Additionally, patients should receive individual, one-on-one treatment and should not participate in group treatment of aggression during data collection.

Because this is a multi-centre study, there are minor differences between the treatment as usual for aggression between the participating clinics and even between participating therapists. To illustrate, some clinics use the 'AR op Maat' program, while others use 'Grip op Agressie' as the main guidelines for their aggression treatment. While there are minor differences in the form of these types of treatment, they are all based on the same underlying principles and models. All forms of treatment in forensic psychiatry target dynamic risk factors that have been identified by means of risk assessment instruments. In general, treatment of patients with aggressive behaviour is always focused on the improvement of self-regulation to reduce the chance of (re)offending. This is achieved by means of elements

from cognitive behavioural therapy, often combined with techniques from occupational therapy.

Furthermore, because the forensic psychiatric patient population is very heterogeneous - with much variation in e.g. diagnoses and type of offense, there is often also variation in the length of treatment and the exact way it is delivered to individual patients, even when following the same protocol. This is done to ensure that treatment is tailored – in forensic terms, responsive – to the individual patient [41]. Consequently, it is unfeasible and undesirable to offer exactly the same TAU to each patients since this is not in line with guidelines and treatment models that are used in practice. Despite the heterogeneity of the patient population and treatment, it is expected that there will be no major differences in outcomes between the different types of treatment because they are all based on the same principles. Forensic treatment in the Netherlands is always focused on risk assessment and management, grounded in evidence-based treatment protocols such as cognitive behavioural therapy, and underpinned by the risk-need-responsivity model. Additionally, all included patients in this study will receive in-person treatment with weekly sessions with their therapist, focused on aggression regulation, and underpinned by principles of cognitive behavioural therapy.

To summarize: while in general terms, treatment of all patients is based on similar principles and guidelines, there will be minor differences in the way in-person treatment will be delivered between patients in both the control and experimental conditions, this is part of the ecological validity of this study and is not expected to influence results because of the randomization.

## **6. INVESTIGATIONAL PRODUCT**

Not applicable. Minddistrict and the 'Aggression' module are already mentioned and explained in chapter 5.

## **7. NON-INVESTIGATIONAL PRODUCT**

Not applicable. This study won't be using any additional products.

### **7.1 Name and description of non-investigational product(s)**

Not applicable.

### **7.2 Summary of findings from non-clinical studies**

Not applicable.

### **7.3 Summary of findings from clinical studies**

Not applicable.

### **7.4 Summary of known and potential risks and benefits**

Not applicable.

### **7.5 Description and justification of route of administration and dosage**

Not applicable.

### **7.6 Dosages, dosage modifications and method of administration**

Not applicable.

### **7.7 Preparation and labelling of Non Investigational Medicinal Product**

Not applicable.

### **7.8 Drug accountability**

Not applicable.

## 8. METHODS

### 8.1 Study parameters/endpoints

In this study, multiple types of data are collected to answer the six research questions. First, a short overview will be provided, after which the specific measurement instruments will be explained in more detail.

The variables for the first research objective – focused on the improvement in regulatory emotional self-efficacy, treatment readiness and aggression – will be collected via short, validated self-report questionnaires that will be administered via Qualtrics. To answer the first research question, three primary outcome measures will be used. The main reason for selecting three outcome measures, is that this is the first RCT on internet-based interventions in forensic outpatient care [16]. Consequently, there are no other RCTs on which the choice for outcome measures can be based. The three main outcome measures are based on qualitative research, combined with insights of therapists and researchers [17, 19, 21, 42]. However, based on these sources, it is not clear which of these outcome measures is best to identify change on the short and long term due to the intervention. The intervention is viewed as potentially effective if the experimental group improves more than the control group on at least one of the outcome measures on T1, T2, and/or T3. The intervention is viewed as effective in case of changes on all three outcome measures on T3.

For the second objective, data from risk assessment instruments that are already administered will be collected at baseline and follow-up. Since risk assessment with the FARE has to be performed twice per year, this form of data collection is in line with existing procedures and thus will not take up additional time of patient and therapist. For the third objective, therapists will be asked to indicate the number of treatment sessions that the patient participated in. Therapists can retrieve these data from their calendar, the electronic patient file or supported by the office assistants, the exact method depending on their own preference. Data for the fourth objective on engagement will only be collected from patients in the experimental condition. The TWEETS engagement questionnaire will be built into the internet-based intervention to ensure that it is filled out at the right point in the intervention, i.e. at the beginning, halfway and at the end. Another reason for this is that, if engagement is a predictor for effectiveness, Minddistrict will integrate the TWEETS in all interventions. The fifth and sixth objective will be addressed by means of qualitative data, collected by means of semi-structured interviews with patients and via questionnaires with open-ended with therapists. Finally, at baseline, patients are asked to fill out several questions on demographics, including their gender, age, marital and employment status and education level. Participants will also be asked if they received forensic and/or regular psychiatric treatment in the past. Additionally, at baseline therapists will be asked to provide information

about the inpatient clinic in which the patient is treated, the main treatment goal, type of offense, and diagnoses. These data will be used to describe the sample and will be collected via Qualtrics.

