While no robust effectiveness studies have been conducted on the use of internet-based interventions in forensic outpatient care, earlier research has provided several useful insights and recommendations. First, a straightforward recommendation is to study the effectiveness of internet-based interventions in clinical practice to gain insight into whether they work [17, 19]. However, merely gaining insight in effectiveness does not fully answer all questions that arise from research and practice. Consequently, a second recommendation is related to the use of these interventions. A recent study on implementation of these internet-based interventions in forensic outpatient care has shown that adherence to them is low: most patients don't complete all lessons of a intervention and a large share drops out after one session [21]. While an important reason for this is that therapists forget to introduce these modules to patients and do not integrate and discuss them in treatment sessions, explanations for non-adherence might also be found in patient characteristics. This highlights the importance of research that determines if and how we can predict if a patient drops out of the intervention. A third recommendation is related to the 'what works for whom' question. Therapists indicate that internet-based interventions do not seem to fit the entire forensic psychiatric population, but can be of added value for some patients. However, this is merely based on clinical experiences and subjective estimations: there has not been research on this topic yet. In other words: up until now, there is no clear explanation of why an

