### ***Engagement – TWEETS***

Many studies have been conducted to identify why and for whom specific internet-based interventions work. Up until now, the use of sociodemographic factors as predictors has not provided answers to these questions. Engagement is a non-specific factor that can be used to predict effectiveness of and adherence to internet-based interventions [46]. Engagement refers to the extent to which someone is involved or occupied with something, and is often related to a positive outcome, such as effectiveness. In the context of digital behaviour change interventions, engagement contains an affective, behavioural and cognitive component [46]. The affective component is focused on positive or negative feelings towards the intervention and the way in which the intervention fits with a person's identity: do people identify with the design of the technology and what it stands for? Behavioural engagement is focused on the routine that a user has regarding the use of an intervention and the extent to which it requires effort and is part of one's daily life. The cognitive component of engagement refers to the extent to which an intervention supports the user in reaching their goals and is seen as useful for their behaviour change.

In this study, engagement is measured with the TWente Engagement with Ehealth and Technologies Scale (TWEETS). The scale employs a definition of engagement that incorporates behaviour, cognition, and affect, and has been shown to have a good validity and reliability [35]. The TWEETS contains only 9 items – with three items per component of engagement - and has three slightly different versions: one for expected engagement, to be used when someone starts using an intervention, one for current engagement, to be used

during the use of an intervention, and one for past engagement, to be used when a user has completed or stopped using an intervention.

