**Step 5: Randomization and start intervention – Week 12**

Directly after the patient has provided informed consent, the patient is randomized by the researcher. This is communicated to the therapist, who will let the patient know whether they will start with the intervention 'Aggression' or if they will participate in the control group.

After the first session of the internet-based intervention is finished, the TWEETS will be administered to participants in the experimental group via the Minddistrict platform, because the TWEETS is integrated in the intervention.

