**Step 6: Mid-treatment assessment (T1) – Week 17**

In order to assess change during the intervention period, the three questionnaires to assess self-efficacy, aggression and treatment readiness are again administered to participants in the control and experimental group in week 17 of the study period. During treatment, the

therapist indicates that the patient can expect the questionnaires in the upcoming week to ensure that the link to the Qualtrics questionnaires is not overlooked. After that, the researcher e-mails the link to the Qualtrics questionnaires to the patient. If the patient did not complete the questionnaire after two days, a reminder is sent via e-mail. If the patient does not fill out the questionnaire after this reminder, the same procedure as in the baseline is followed.

Furthermore, the TWEETS is again administered, following the same procedures as at T0. Finally, participants will receive the first €10 voucher after completing the baseline assessment via e-mail.

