### ***Step 7: Assessment post-intervention (T2) – Week 25***

After 15 weeks, the three questionnaires on self-efficacy, aggression and treatment readiness will be administered again, following the same procedures as described before. Furthermore, after finishing the final lesson of the intervention, the patient will fill out the TWEETS on the Minddistrict platform.

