### ***Step 8: Qualitative data collection with patients - Week 25 – 30***

After the intervention is completed, a randomly selected sample of patients is invited to participate in a post-intervention interview. This sample is generated by means of (<https://sealedenvelope.com/>). Because the perspective of patients who dropped out of the intervention also is very relevant, the target group of this interview study will consist of patients who completed at least one session of the intervention, i.e. who completed the first TWEETS. Additionally, patients still have to be treated at the outpatient clinic in order to participate. Semi-structured interviews will be conducted in-person or via videoconferencing, depending on the preference of the patient and practical limitations.

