### ***Research objective 4: Engagement***

To investigate whether engagement predicts effectiveness, simple linear regression analyses will be run for three variables: regulatory emotional self-efficacy, treatment readiness, and aggression. The score on the TWEETS on T0, T1 and T2 will be used as independent variables in three different regression analyses. The change scores (i.e. difference between scores on T2 and T0, and the difference between scores on T3 and T0) for all relevant variables (self-efficacy, treatment readiness and aggression) will be used as dependent variables for two regression analyses. These scores will be added in a second analysis to

measure whether it adds predictive value on the dependent variables. Furthermore, in order to investigate if the TWEETS scores predict adherence, three analyses with the TWEETS score on T0 and T1 as dependent variables are run, this time with the number of finished lessons of the intervention as dependent variable.

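### TWEETS is triggered by lesson progress, so patients who stop the module lack halfway and end scores, and the halfway-score regression on finished lessons is truncated on its own outcome

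*Combined protocol and SAP*

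**What the plan says.** **Delivery.** Section 8.1 states: "The TWEETS engagement questionnaire will be built into the internet-based intervention to ensure that it is filled out at the right point". The points named there are the beginning, halfway and end of the module. Section 8.3 gives the triggers:

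- First score (Step 5): "After the first session of the internet-based intervention is finished, the TWEETS will be administered to participants in the experimental group via the Minddistrict platform".
- Halfway score (Step 6): "the TWEETS is again administered, following the same procedures as at T0".
- End score (Step 7): "after finishing the final lesson of the intervention, the patient will fill out the TWEETS on the Minddistrict platform".

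Step 8 describes its interview group as "patients who completed at least one session of the intervention, i.e. who completed the first TWEETS", which treats having a score and finishing a lesson as the same thing. Section 8.1.2 says the scale has three versions, including "one for past engagement, to be used when a user has completed or stopped using an intervention". No section describes a route by which a patient who stops early would receive that version.

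**Analysis.** Under Research objective 4, section 10.2 regresses the T2–T0 and T3–T0 changes in the three outcomes on TWEETS at T0, T1 and T2. Then, "in order to investigate if the TWEETS scores predict adherence", it takes the number of finished lessons as outcome and names the T0 and T1 scores. It announces three such analyses but names two scores, and it calls both sides of the model dependent. It gives no rule for a missing TWEETS. The missing-data remark in section 10.1 concerns the mixed model for objective 1.

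**Expected use.** Of earlier practice, section 1 reports that "most patients don't complete all lessons of a intervention and a large share drops out after one session". Sections 4.4 and 8.6 say that stopping the module is not study drop-out as long as the questionnaires are completed.

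**The concern.** Whether a patient has a halfway or end score depends on how many lessons that patient finished. Patients who stop early leave those regressions because they stopped, and they are the patients section 1 wants to be able to identify.

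For adherence, the halfway model relates engagement to lessons finished only among patients who already have about half of them. The lower part of the outcome is removed by design, and the association shrinks. For effectiveness, the halfway and end models describe patients who reached that point, on a smaller sample.

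The result has a stated use: section 8.1 says the developer will build TWEETS into all its interventions if engagement predicts effectiveness. A weak halfway or end association could then be read as evidence about engagement in general. Scores never collected from patients who stopped cannot be recovered at analysis.

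**Working it through.** **1. The plan's own figure.** Section 4.4 uses d = 0.5, two-sided 5% and 80% power. The t-test calculation gives 63.77, so 64 per arm and 128 in total. 128 × 1.2 = 153.6, so 154, as stated. With equal arms (implied by 64 in each condition), the experimental arm has 154 / 2 = 77. After 20% drop-out, 77 × 0.8 = 61.6, about 62. The plan gives no sample size or power for objective 4.

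**2. Who has a score (assumed).** The documents give no usage percentages and do not name the halfway lesson; I take lesson 5.

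- 50–70% reach lesson 5: 77 × 0.50 = 38.5 and 77 × 0.70 = 53.9, so 38 to 54 halfway scores.
- 30–55% finish: 77 × 0.30 = 23.1 and 77 × 0.55 = 42.4, so 23 to 42 end scores.

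**3. Power for r = 0.30** (two-sided 5%, Fisher z): power = Φ(atanh(0.30) × √(n − 3) − 1.96), with atanh(0.30) = 0.3095.

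| Patients with a score | n | 0.3095 × √(n − 3) | Power |
|---|---|---|---|
| All experimental | 77 | 2.663 | 76% |
| All, after 20% drop-out | 62 | 2.377 | 66% |
| Halfway, 70% reach | 54 | 2.210 | 60% |
| Halfway, 50% reach | 38 | 1.831 | 45% |
| End, 55% finish | 42 | 1.933 | 49% |
| End, 30% finish | 23 | 1.384 | 28% |

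The halfway and end rows are before study drop-out, so their direct comparator is 76%. These figures hold r fixed and show loss of sample only.

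**4. Truncation of the adherence model.** Engagement and a latent tendency to continue were simulated as bivariate normal with correlation 0.3 or 0.5. Lessons finished were set by assumed completion curves, and the correlation of engagement with lessons was taken in each subgroup.

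| Finish lesson 1 / reach 5 / finish 10 | Latent correlation | All | Has first score | Has halfway score |
|---|---|---|---|---|
| 95 / 70 / 50% | 0.3 | 0.26 | 0.23 | 0.14 |
| 90 / 50 / 30% | 0.3 | 0.28 | 0.23 | 0.13 |
| 80 / 30 / 15% | 0.3 | 0.28 | 0.22 | 0.12 |
| 95 / 70 / 50% | 0.5 | 0.44 | 0.39 | 0.24 |
| 90 / 50 / 30% | 0.5 | 0.46 | 0.40 | 0.23 |
| 80 / 30 / 15% | 0.5 | 0.47 | 0.38 | 0.21 |

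Raising the share who finish to 55% (95 / 70 / 55%) gives 0.26 to 0.12 and 0.43 to 0.21 at halfway. Over all curves the fall is from 0.26–0.47 to 0.12–0.24. The halfway slope falls by about three quarters: for example 0.943 to 0.221 lessons per SD of engagement, and 1 − 0.221/0.943 = 77%.

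**5. Effectiveness slopes.** With an assumed direct effect of engagement of 0.3 and a further effect of lessons of 0.3 per SD, the slope is 0.38–0.44 in all patients, 0.32–0.34 in those with a halfway score and 0.30 in finishers. With no lesson effect it stays at 0.30 in every subgroup. A fall therefore depends on the model assumed.

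**The case against.** The strongest reply is that the first TWEETS rescues the objective. It comes after lesson 1, and section 10.2 uses it for both adherence and effectiveness. Patients who leave after one session, the group section 1 describes, would have it. The simulated loss there is small: 0.26–0.28 to 0.22–0.23, and 0.44–0.47 to 0.38–0.40. This stands. A reader might infer that objective 4 is answered only in adherent patients, or that a null result must be an artefact of collection. The documents do not support either.

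A reader might also infer that the adherence model on the end score cannot be estimated because every finisher has ten lessons. That would be true of such a model, but section 10.2 names only the T0 and T1 scores for adherence. The announced third analysis makes this unclear, not settled.

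Nor is bias toward zero established for effectiveness. Selection on the predictor lowers precision and r, but biases a linear slope only under further assumptions, such as an effect of lessons on outcome.

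The low use reported in section 1 is earlier practice, and this trial adds therapist reminders (sections 4.5 and 8.2), so reach could be better than assumed. Measuring at module milestones is a reasoned choice for a secondary, single-arm objective.

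Step 6 stands under week 17 and Table 1 lists T1, so a calendar reading of the halfway score is possible. The stated procedure and section 8.1 point to delivery in the module; at the least these places need reconciling.

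**Conclusion.** The point holds for the halfway and end scores. The regression of finished lessons on the halfway TWEETS is truncated on its own outcome. The effectiveness regressions on the halfway and end scores include only patients who got that far. The direction of the adherence effect and the loss of sample follow from the delivery route. Their size rests on assumed reach, assumed correlations and halfway taken as lesson 5.

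For effectiveness, what is certain is fewer patients and a result that does not extend to those who stopped. The regressions on the first TWEETS remain largely usable, although patients who never finish lesson 1 have no score there. The primary comparison is untouched. The sponsor should make the change because it is cheap; it does not threaten the trial's main conclusion.

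**What to change.** **Collection.** Keep the in-module TWEETS. Add the 9 items to the T1 and T2 Qualtrics links for every experimental patient who has not completed the in-module questionnaire due at that time. Record whether the current or the past version was used, and state which score counts if a slow patient later completes the in-module one.

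**Effectiveness models (section 10.2).** Use these scores at T1 and T2, with TWEETS version as a covariate or in a sensitivity analysis. State how missing scores are handled and report how many patients have a score at each point.

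**Adherence models.** Make the first TWEETS the main predictor of finished lessons. Use the halfway score only to predict lessons completed afterwards, among patients still using the module, and report that result as conditional on reaching that point. Do not use the end score or the past version to predict adherence: patients who have stopped have almost no later lessons to predict, so including them would build in an association. Correct the wording on the number of analyses and on which variable is dependent.

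**Cost.** Up to about 5 minutes per time point for patients who stopped, within the 5 minutes per TWEETS (15 in total) that Table 1 already allows the experimental group, plus two questionnaire additions and revised analysis text. Some patients will not respond, so the gain will be less than the full step back to 76% or 66% power. The versions differ slightly, and version will be partly confounded with stopping, which is why it must be recorded. The change has to be made before or during data collection. If it is not made, the plan should at least present the halfway and end analyses as conditional on reaching that point.
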